Opioid-related overdose deaths have quadrupled since 1999 making drug overdose the new leading cause of accidental death in the U.S.¹ The current practice of providing emergency department (ED) patients who endorse opioid use disorder (OUD) with only a referral to local treatment programs, which often have long waiting lists, represents a tragic missed opportunity to engage patients in sustained medical care.^{2,3} We hypothesize that a novel intervention at the UVM Medical Center (UVMMC), which will 1) initiate buprenorphine treatment in patients presenting at the ED with OUD, and 2) guarantee enrollment in the UVMMC Addiction Treatment Program (ATP) within 24 to 72 hours, will address the acute crisis period when individuals are most vulnerable to relapse and lead to increased long-term participation in Medication-Assisted Treatment (MAT). This project is expected to generate immediate benefits for those enrolled and will provide proof of concept evidence for a new model of engaging individuals with OUD in long-term care.

Vermont has a lower rate of fatal opioid overdoses than the national average and a significantly lower rate than other rural New England states (e.g. 13.9 deaths per 100,000 in Vermont compared to 26.2 in New Hampshire in 2014).⁴ This situation has been attributed to the development of an effective "Hub and Spoke" OUD treatment system and proactive state-sponsored programs to increase access to emergency opioid overdose rescue kits and needle exchanges.^{4,5} Despite this, the number of drug-related fatalities in Vermont continues to increase in parallel with the alarming national upward trend, surging 37% from 2015 to 2016.⁶ Thus, the Vermont response to the opioid epidemic urgently requires further improvement to address a still growing problem. A key challenge in addressing OUD is that most individuals who would benefit from a medical intervention do not receive any assistance. Only 10.8% of the estimated 21.7 million people in the U.S. with a past year substance use disorder received specialized treatment.⁷ Consequently, the presentation of patients with OUD at the ED is a critical

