opportunity to identify individuals in need and direct them toward long-term treatment programs. The current standard of care for individuals with OUD presenting to the ED provides management of acute symptoms and contact information for treatment programs, which often have long waiting lists.³ Here, we will compare the standard practice with a novel intervention that will provide 1) immediate initiation of buprenorphine treatment at the ED and 2) guaranteed placement in a specialized OUD treatment program (i.e. UVMMC Addiction Treatment Program -ATP) within 24 to 72 hours after discharge. The primary outcome measure will be opioid use at 1 week and 3 & 6 months after buprenorphine initiation.

Aim 1. To determine whether ED-initiated buprenorphine treatment coupled with enrollment in a bridge clinic that will supervise MAT until the patient is stabilized and placed with a local MAT provider will reduce illicit opioid use compared to ED-initiated buprenorphine treatment coupled with immediate referral to a local MAT provider.

Hypothesis: Patients assigned to the ED-initiated buprenorphine plus ATP bridge clinic intervention will have significantly reduced illicit opioid use as determined by urine drug screen at 1 week, and 3 & 6 months than patients who only receive direct referral to a local MAT provider. .

PURPOSE AND OBJECTIVES

Purpose: *The importance of the research and the potential knowledge to be gained should be explained in detail. Give background information.*

The explosive increase in opioid use in the U.S. over the past two decades poses a formidable threat to the national welfare.¹⁰⁻¹³ In the last month, an estimated 400,000 individuals have used heroin and over four million individuals have used prescription pain medication for non-medical purposes.^{14,15} The latest estimates released by the CDC for the year 2016 indicate that a dramatic surge in opioid related deaths has produced a population level decline in average life expectancy.¹⁶ Opioid-related overdose fatalities have quadrupled since 1999.¹ In 2016 alone, 63,200 Americans died of an opioid-related overdose, which represents a 21% increase over the preceding year. The rapid development of evidence-based approaches to manage the opioid epidemic is critical at this time. Here, we will examine whether an ED-initiated intervention will lead to lower rates of opioid use and higher enrollment in medical treatment for OUD.

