Here, we will investigate whether ED-initiated MAT with buprenorphine and sustained clinical follow-up for patients presenting with OUD at ED lowers opioid use and increases retention in treatment. Preliminary evidence suggests that ED-initiated MAT will produce positive short-term outcomes. In a randomized trial, opioid dependent patients receiving ED-initiated buprenorphine treatment with 10 weeks of supervised MAT were significantly more likely to be enrolled in a treatment program at 30 days after study recruitment than patients who only received a simple referral (i.e. 95% vs. 37%, respectively).⁸ Retention rates remained elevated at 2 months.⁹ However, these effects had completely disappeared by 6 and 12 months. We believe that the long-term failure of this intervention at 6 and 12 months was due to lack of opportunity for most participants to continue supervised MAT after the end of the study. The present study will examine whether ED-initiated MAT combined with sustained clinical supervision at ATP, which monitors patients until they transfer to long-term care, results in lower rates of opioid use. ED-initiated treatment for OUD would mirror immediate treatment of other chronic life-threatening diseases presenting to the ED.

INNOVATION

- Integration of ED-initiated buprenorphine treatment with sustained treatment follow-up at ATP, a MAT bridge clinic.
- ATP will eliminate the treatment waitlist for study participants and effectively bridge the critical relapse period between the ED visit and entry into long-term treatment.

Impact: The ED initiated buprenorphine treatment and ATP intervention is expected to effectively bridge the risk of relapse in the critical period between ED presentation and integration into the standard Vermont Hub-and-Spoke system for monitoring long-term MAT. Opioid use disorder contributes to frequent re-admission rates in certain patients. Improving the chances that these individuals enroll in long-term care will reduce ED burden and free up resources for other patients. Positive findings on Aim 1 will support network-wide adoption of this intervention in Vermont.

References. Include references to prior human or animal research and references that are relevant to the design and conduct of the study.

- 1 CDC. Wide-ranging online data for epidemiologic research (Wonder). (CDC, National Center for Health Statistics, Atlanta GA, 2016).

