Objectives: Clearly state the primary and secondary objective(s) of the study.

The primary outcome will be urine specimens for illicit opioids at 1 week and 3 & 6 months after ED initiated treatment. Urine specimens will be collected under observation of same-sex staff and immediately analyzed for opioids (buprenorphine, methadone, oxycodone, hydrocodone, hydromorphone, heroin, fentanyl) and other drugs (cocaine, amphetamines, benzodiazepines, cannabinoids) via enzyme multiplied immunoassay. Missing urine specimens will be considered positive for illicit opioids, consistent with an intent-to-treat approach.

[figure not shown]
Secondary outcomes will include self-reported illicit opioid or other (non-opioid) drug use, treatment enrollment status and behavioral questionnaires (i.e. the GPRA Client Outcome Measures questionnaire, the Treatment Effectiveness Assessment (TEA),⁴³ and the Vermont Treatment Needs Questionnaire (TNQ)²¹).

METHODS AND PROCEDURES

Study Design: Describe the research design, including a description of any new methodology and its advantage over existing methodologies.

This pilot project will test whether ED-initiated buprenorphine treatment for individuals presenting to the UVMMC ED with OUD combined with a MAT bridge clinic leads to a reduction in illicit opioid use at 1 week, and 3 & 6 months compared ED-initiated treatment with a direct referral to a local MAT provider. The intervention and study design include 5 main stages (see figure below): 1) Patients admitted to the ED with indicators of OUD will be consented and screened for study eligibility; 2) Participants will undergo buprenorphine induction at the ED; 4) Participants enrolled at Central Vermont Medical Center and Porter Medical Center will be referred directly to a local MAT provider. Participants enrolled at UVMMC will be referred to the UVMMC ATP, a MAT bridge clinic that will supervise MAT with buprenorphine in all participants who enroll in the program until the individual is transferred to a long-term MAT provider, referred to a higher level of care or drops out of treatment --treatment duration at ATP is typically 8 weeks before referral of stable patients to primary care providers; 5) All participants will be contacted at 1 week, and 3 & 6 months after randomization to determine current illicit opioid use.

We expect to enroll 200 participants over 3 years.

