Part 5) Outcome Assessment. The primary outcome will be illicit opioid use at 1 week and 3 & 6 months after buprenorphine induction. Consistent with standard ATP practice, urine sample collection and analysis will be performed by Aspenti Labs (<https://www.aspenti.com/>), a clinical drug testing service which is open Monday to Friday 7AM-7PM and has multiple locations throughout Vermont. Urine specimens will be collected under observation of same-sex staff and analyzed for opioids (buprenorphine, methadone, oxycodone, hydrocodone, hydromorphone, heroin, fentanyl) and other drugs (cocaine, amphetamines, benzodiazepines, cannabinoids) via enzyme multiplied immunoassay. Missing urine specimens will be considered positive for illicit opioids, consistent with an intent-to-treat approach. Additional outcomes will include self-reported illicit opioid or other (non-opioid) drug use, treatment enrollment status and behavioral questionnaires (i.e. the GPRA Client Outcome Measures questionnaire to track self-reported drug-use and life conditions). The Treatment Effectiveness Assessment (TEA)⁴³ will be included at 1 week, 3 months and 6 months to track patient perception of treatment progress. Additional follow-up questions based on the PhenX toolkit are attached.

Retention. Participating in OUD treatment has health advantages for the participants which is a motivation to remain in the study. Participants will receive a \$25 gift card after answering questionnaires in Step 11. In addition, as an incentive to provide a urine sample and answer questions at follow-up, participants will receive a \$25 gift card for answering questions by phone and a \$50 gift card for a urine sample at each of the three outcome time points completed (i.e. 1 week, 3 and 6 months post randomization). In total, participants can earn up to \$250 for their participation in the study. To avoid altering the motivation to stay in MAT, participants will earn payment for providing the urine samples and answering questions at each of the 3 follow-up time points, regardless of whether they are currently in treatment. Missing urine specimens will be considered positive for illicit opioids, consistent with an intent-to-treat approach.

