Follow up questionnaire (attached) based on PhenX drug use history toolkit takes approximately 105 minutes to complete TEA takes approximately 5 minutes to complete

The GPRA Client Outcome Measures questionnaire takes approximately 30 minutes to complete.

Baseline questionnaires will be administered on an iPad by the EMRAP staff or the study RA in patient care areas or by phone.

At 1 week, 3 months and 6 months, questionnaires will be administered by the study RA by phone. Participants may be contacted in advance by text or email to arrange a time for the call that is convenient for the participant.

Questionnaires will be labelled with the participant's unique study ID number and stored separately from identifiable information (e.g. name, address, phone number etc).

Statistical Considerations: Delineate the precise outcomes to be measured and analyzed. Describe how these results will be measured and statistically analyzed. Delineate methods used to estimate the required number of subjects. Describe power calculations if the study involves comparisons. Perform this analysis on each of the primary and secondary objectives, if possible.

200 hundred individuals will be recruited to the study over the course of 3 years.

The primary outcome measure will be illicit opioid use at 1 week and 3 & 6 months.. Group differences (i.e. with or without the MAT bridge clinic) in opioid use will be assessed by logistic regression at each of the three time points. A power analysis using G*Power50 indicates that a medium effect size, e.g. 0.3, related to the comparison of illicit opioid use in the experimental and control groups will be correctly identified with a power of 0.93 in a total sample of 200 individuals. Statistical tests will be performed in SPSS Statistics for Windows, Version 21.0. (Armonk, NY: IBM Corp). Logistic regression will be one-tailed with significance defined as $p < 0.05$.

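### The primary outcome is tested at three time points, each one-tailed at 0.05, with no rule for success; if any one counts, multiplicity alone gives about 8–14% false positives

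*Combined protocol and SAP*

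**What the plan says.** Under Statistical Considerations the primary outcome is illicit opioid use at 1 week, 3 months and 6 months. Group differences are to be "assessed by logistic regression at each of the three time points". The error rate is set per test: "Logistic regression will be one-tailed with significance defined as" p < 0.05. One power figure is given, for an effect size of 0.3 that "will be correctly identified with a power of 0.93 in a total sample of 200 individuals".

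The other places that define the outcome treat the three time points as equals:

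- Objectives: "The primary outcome will be urine specimens for illicit opioids at 1 week and 3 & 6 months after ED initiated treatment".
- Part 5) Outcome Assessment: "The primary outcome will be illicit opioid use at 1 week and 3 & 6 months after buprenorphine induction".
- Aim 1, Hypothesis: bridge-clinic patients will have "significantly reduced illicit opioid use as determined by urine drug screen at 1 week, and 3 & 6 months".

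Withdrawal Procedures adds that the study urine tests at these three times will decide whether the intervention succeeded, without saying how. None of these places gives a primary time point, testing order, alpha split, joint or repeated-measures test, or an any/all rule.

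**The concern.** Three tests feed one verdict on Aim 1, and the plan does not say how they combine. The text allows two readings. Under the first, significance at any one time point makes Aim 1 positive, and the false-positive rate exceeds 5%. Under the second, all three must be significant; the error is controlled, but power must be stated for the joint result.

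The choice affects the conclusion. The Impact paragraph says: "Positive findings on Aim 1 will support network-wide adoption of this intervention in Vermont". What counts as positive should therefore be fixed beforehand. A mixed result is plausible: the Purpose section describes an earlier trial whose gain in treatment retention was present at 2 months and gone by 6. The rationale does not settle which time point matters most. The opening summary stresses "the acute crisis period when individuals are most vulnerable to relapse", which points to 1 week, and in the same sentence long-term participation in treatment, which points to 6 months.

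**Working it through.** **Inputs.** Three tests, each one-tailed at 0.05 (Statistical Considerations), so the critical value is z = 1.645. Total N = 200 with 140 at UVMMC (Number of Subjects), leaving 200 − 140 = 60 at the referral sites. The correlation r between the three test statistics is not given; I take a common r from 0 to 0.9.

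**The plan's own figure.** The stated power of 0.93 does not follow from the stated inputs for a two-group comparison of a binary outcome. The metric of the effect size 0.3 is not stated, so I tried several:

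- Cohen's h (one-tailed 0.05), 100/100: mean of the statistic 0.3 × √(100 × 100/200) = 2.121; power Φ(2.121 − 1.645) = 0.68.
- Cohen's h (one-tailed 0.05), 140/60: 0.3 × √(140 × 60/200) = 1.944; power Φ(1.944 − 1.645) = 0.62.
- Chi-square w, 1 df: 0.3 × √200 = 4.243; power 0.995 one-tailed, 0.989 two-sided.
- Chi-square w, 5 df, alpha 0.05: 0.927, which rounds to 0.93, but 5 df does not fit two groups and a binary outcome.

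I report 0.93 as not reproduced and use it below only as an illustration. The error rates do not depend on it.

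**False positives, no effect at any time point.** With independent statistics, P(at least one) = 1 − 0.95³ = 0.1426, and P(all three) = 0.05³ = 0.0001. With common correlation r,

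P(none) = ∫ φ(u) · Φ((1.645 − √r·u)/√(1 − r))³ du,

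P(at least one) = 1 − P(none), and P(all three) is the same integral with the upper tail in place of Φ.

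| r | At least one | All three | At least one, each test at 0.05/3 |
|---|---|---|---|
| 0 | 14.3% | 0.01% | 4.9% |
| 0.3 | 13.0% | 0.17% | 4.6% |
| 0.5 | 11.8% | 0.50% | 4.3% |
| 0.7 | 10.3% | 1.15% | 3.8% |
| 0.9 | 8.0% | 2.5% | 2.9% |

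At r = 0.95 the chance of at least one is 7.1%, so 8% is the value at 0.9 and not a floor. The bound for the all-three rule is 5%, approached when two time points have true effects and the third has none.

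**Missing specimens counted as positive.** This rule carries early losses into later visits and so tends to raise the correlation. In 40,000 simulated trials of 140/60 with no group effect (assumed: 50% positive if observed; cumulative missing 10%, 25% and 35%; latent correlation 0.3 to 0.7), the test statistics correlated at 0.20 to 0.53 and the chance of at least one false positive was 11.9% to 12.6%.

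**Power under each rule.**

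- All three required, 0.93 per time point taken as given: each statistic has mean 1.645 + 1.476 = 3.121. Joint power is 0.80, 0.82, 0.84, 0.86 and 0.89 at r = 0, 0.3, 0.5, 0.7 and 0.9.
- Holm's first step, at 0.05/3 = 0.0167 one-tailed (critical value 2.128): Φ(3.121 − 2.128) = 0.84 per time point on the stated figure. With h = 0.3 and 140/60, Φ(1.944 − 2.128) = 0.43, down from 0.62. With w = 0.3 and 1 df, 0.98, down from 0.995.

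**The case against.** The strongest reply is that the Aim 1 hypothesis lists all three time points together and reads most naturally as requiring all of them; then the error is at most 5%, and no passage says that one is enough. This reading is fair, but the hypothesis does not say that all three must be significant, the analysis section treats the tests as separate, and the single power figure does not describe a joint requirement. What stands is that the inflation is conditional on the any-one reading, and that an explicit all-three rule would also close the gap.

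Second, this is a pilot, and Potential Benefits says its results are meant to support a larger funded programme. That lowers the weight of strict familywise control. The same paragraph repeats the network-wide adoption claim, so a definition of positive is still needed.

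Third, making 6 months primary would let a null result there block a claim at 1 week, and part of the long-term rationale concerns treatment participation, a secondary outcome. This stands as a reason for the investigators to choose and justify the time point themselves.

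Fourth, the groups are defined by hospital, so even one test's 5% is not assured. That is true but separate; the figures here cover multiplicity only.

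**Conclusion.** The concern holds. As written, the plan lets the same three results be called a success or a failure after they are seen. If any one significant time point counts, the false-positive rate from multiplicity is about 8% to 14% for correlations from 0.9 down to 0, and about 12% under the missing-data assumptions tried. If all three are required, it is at most 5%, and power must be restated. The range rests on an assumed common correlation, approximately normal test statistics and no group effect at any time point. This should be fixed, but it does not call for any change in how the trial is run.

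**What to change.** Before outcome data are examined, write one rule into Objectives and Statistical Considerations.

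(a) Preferred: one primary time point, with the others in fixed order. For example: *The primary analysis is illicit opioid use at 6 months; 3 months and then 1 week are each tested at one-tailed 0.05 only if the preceding test is significant.* Six months is one choice consistent with the long-term rationale; the investigators may justify another. This keeps full alpha and power at the primary time point. The cost is that a benefit seen only at another time point can no longer carry the claim.

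(b) Or keep all three as primary and apply Holm at overall one-tailed 0.05. The cost is first-step power per time point: 0.93 to 0.84 on the stated figure, 0.62 to 0.43 if 0.3 is Cohen's h with 140/60, and very little if it is chi-square w with 1 df.

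If the investigators meant that all three must be significant, stating so also controls the error, at the cost in joint power shown above.

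Whichever rule is chosen, state the effect-size metric and restate power for that rule. Two-sided testing is optional and not part of this point: a one-tailed test still estimates an odds ratio in either direction, but cannot declare a significant difference against the bridge clinic.

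No new data are needed. The change is a protocol amendment made while UVMMC enrolment continues, so it should record that outcomes had not been examined when the rule was set.
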